5.1. Administration schedule to Patients (Transplant recipients)

1. Atorvastatin will be administered at dose of 40mg orally daily starting on day -14, to permit an approximately 1-week observation period to rule out any acute atorvastatin-induced side effects before the initiation of transplant conditioning.
2. Patients who have previously been taking atorvastatin or any other statin drug will be eligible as long as there is no contraindication to switch to atorvastatin (40mg/day) in the opinion of the treating physician.
3. Patients undergoing myeloablative conditioning (MAC) matched sibling or unrelated donor allogeneic transplantation can receive one of following three conditioning regimens:
 - a) Busulfan ≥ 0.8 mg/kg/dose (16 doses given every 6 hours, IV on days -7 to -4), and cyclophosphamide 60 mg/kg/dose (2 doses given every 24hours, IV on days -3 and -2). Monitoring busulfan levels with this regimen, per institutional practice, is recommended. Oral busulfan is not permitted.
 - b) Total body irradiation (>500 cGy) and cyclophosphamide as above.
 - c) Total body irradiation (≥ 1200 cGy) and etoposide.
 - d) Other ablative regimens will be permitted after consultation with study PI.
4. Patients undergoing reduced-intensity conditioning (RIC) matched sibling or unrelated donor allogeneic transplantation will receive one of following three regimens:
 - a) Fludarabine and IV busulfan-based regimen (Flu/Bu2 or Flu/Bu4).
 - b) Fludarabine and low dose total body irradiation (200-400cGy)
 - c) Fludarabine and melphalan (≤ 140 mg/m²)
 - d) Other RIC will be permitted after consultation with study PI.

In addition to atorvastatin, standard GVHD prophylaxis will consist of: Tacrolimus (0.015 mg/kg I.V **every 12 hours** or 0.03 mg/kg/day PO; starting day -2) and mini-dose methotrexate (5mg/m² on days +1, +3, +6 and +11). Tacrolimus will be monitored to keep levels between 5-12 ng/ml for matched sibling and between 8-12 ng/ml for unrelated donor HCT. In absence of acute GVHD, renal insufficiency and disease relapse/progression it is recommended that tacrolimus taper **SHOULD NOT** commence before day +100. The goal of tapering is the complete discontinuation of immunosuppressive medications by (but not before) day +180. Tacrolimus should be tapered every two to three weeks. Attempt should be

made to apply similar reductions in dosages at each tapering event, to allow complete discontinuation of immunosuppression by day +180. It is recommended by not required that tacrolimus dose be reduced by no more than 25% at each tapering event.

5. Administration of cyclosporine (because of associated risk of myopathy with atorvastatin), mycophenolate mofetil, monoclonal (e.g. campath) or polyclonal antibodies (e.g. antithymocyte globulin) will not be permitted for GVHD prophylaxis.
6. Antibiotic prophylaxis will be given according to institutional guidelines.
7. Temporary interruption (\leq 10-14days) of atorvastatin is permitted in patients unable to tolerate oral intake secondary to severe nausea, vomiting, mucositis etc. Administration of atorvastatin via feeding tubes is permitted. In case atorvastatin therapy is interrupted, the time interval should be recorded.
8. Toxicity will be evaluated according to CTCAE v4.0.
9. Progression free survival (PFS) and overall survival (OS) following transplantation will be recorded.

5.2. Dose modification

1. Patients experiencing a grade 3-4 hematological or non-hematological toxicity (as specified in CTCAE v4.0) thought to be related to atorvastatin will be removed from the study permanently. No dose modifications for atorvastatin are permitted.
2. Decision to hold atorvastatin in patients developing grade 3-4 liver function abnormalities (bilirubin, AST and ALT) post-HSCT will be at the discretion of treating physician. In such patients if liver function abnormalities are thought not be related to the study drug, then atorvastatin prophylaxis can be restarted at time of resolution of hepatic transaminases (to grade 1 or less) after consulting with principal investigator.

5.3. Duration of therapy

Atorvastatin will be continued until one of the following criteria is met:

- Patient is no longer on immunosuppressive medications or until day +180 after transplantation, whichever occurs first.
- Patient develops grade II-IV acute GVHD.
- Patient develops severe chronic GVHD.

- Patient develops any grade 3-4 toxicity related to atorvastatin use.

Patients experiencing a disease relapse (before day +180) can continue atorvastatin at the discretion of treating physician, provided the patient has not been tapered off of tacrolimus.

5.4. Data Safety Monitoring Plan

At West Virginia University: This protocol will adhere to the policies of the Mary Babb Randolph Cancer Center Data and Safety Monitoring Plan, guidelines in accordance with NCI regulations. The Data and Safety Toxicity Committee (DSTC) will review all serious adverse events and toxicity reports as well as continuing reviews. This study is designated as a **moderate risk level** and requires **quarterly** summary reporting to the DSTC.

At Medical College of Wisconsin: The Medical College of Wisconsin Cancer Center Data Safety Monitoring Committee (DSMC) is responsible for monitoring data quality and subject safety for all cancer center investigator initiated clinical trials. A six to eight member Data and Safety Monitoring Committee will complete a review of protocol-specific data safety monitoring reports, to provide recommendations on trial continuation, suspension or termination. The DSMC will review these reports no less than bi-annually. A summary of the DSMC activities are as follows

- Review the clinical trials for data integrity and safety
- Review all adverse events requiring expedited reporting as defined per protocol
- Review all DSM reports
- Submit a summary of any recommendations related to study conduct
- Terminate the study if deemed unsafe for patients

6. Measurement of Effect:

6.1. Visit Schedule:

The schedule for the study is shown in the table below.

Study Visit	Target Day Post-Transplant
1 week	7 ± 3 days
2 week	14 ± 3 days

3 week	21 ± 7 days
4 week	28 ± 7 days
5 week	35 ± 7 days
6 week	42 ± 7 days
7 week	49 ± 7 days
8 week	56 ± 7 days
9 week	63 ± 7 days
10 week	70 ± 7 days
11 week	77 ± 7 days
12 week	84 ± 7 days
100 day	100± 7 days
6 month	180 ± 28 days
12 month*	365 ± 28 days

*After 12months, patients will be followed at least yearly for survival, relapse and cause of death for 5 years post transplantation.

6.2. GVHD Assessment:

Following neutrophil engraftment, patients will be monitored for development of acute and chronic GVHD at once a week until day +100. After Day 100, patients will be assessed at each study visit for the presence of GVHD. Diagnosis of acute GVHD will require biopsy confirmation in at least one involved organ. When more than one organ is involved, biopsy confirmation of all involved organs is recommended but not necessary. Liver-only GVHD must be confirmed by biopsy. Acute GVHD will be assessed by consensus criteria (Appendix A) (32) and graded on BMT CTN MOP suggested grading sheets (Appendix A). Acute GVHD assessment and grading will be performed by **treating physicians**. Chronic GVHD diagnosis and grading will be according to NIH Criteria. Please see Appendix B (33-34).

Clinical Grading of Chronic GVHD (According to Appendix B)

None

Mild chronic GVHD involves only 1 or 2 organs or sites (except the lung: see below ‡), with no clinically significant functional impairment (maximum of score 1 in all affected organs or sites)

Moderate chronic GVHD involves: (1) at least 1 organ or site with clinically significant but no major disability (maximum score of 2 in any affected organ or site) or (2) 3 or more organs or sites with no clinically significant functional impairment (maximum score of 1 in all affected organs or sites). ‡A lung score of 1 will also be considered moderate chronic GVHD.

Severe chronic GVHD indicates major disability caused by chronic GVHD (score of 3 in any organ or site). ‡A lung score of 2 or greater will also be considered severe chronic GVHD.

6.3. Engraftment Assessment:

Neutrophil engraftment will be defined as first of three consecutive days with ANC $\geq 500 \times 10^9/L$ post-conditioning regimen induced nadir. Similarly platelet engraftment is defined as first day of platelet count $\geq 20,000 \times 10^9/L$, without transfusion for 7 consecutive days. Lineage specific chimerism analysis (CD3 and CD33 subsets), quantitative immunoglobulins and immune reconstitution will be performed on days +28, +100, +180 and +365.

7. Study Parameters (Study Calendar):

7.1. Patient Study Calendar:

The table below summarizes the patient clinical assessments over the course of the study.

Study Assessment	Baseline ¹	Day-14	Day0	Days Post-Transplantation														
				7	14	21	28	35	42	49	56	63	70	77	84	100	180	365 ¹⁵
Informed consent and H & PE ²	X						X					X				X	X	X
Vital signs ³	X	X	X				X					X				X	X	X
Karnofsky performance status	X						X					X				X	X	X
CBC/differential & platelet count	X		X	X ⁴	X ⁴	X ⁴	X ⁴					X				X	X	X
Serum chemistries panel ⁵	X		X	X	X	X	X					X				X	X	X
Infectious disease titer ⁶	X																	
LVEF ⁷	X																	
DLCO	X																	
CMV quantitative PCR						X	X	X	X	X	X	X	X	X	X	X	X	
Bone marrow aspirate/biopsy ⁸	X															X	X	X
B-HCG serum pregnancy test ⁹	X																	
Quantitative immunoglobulins ¹⁰							X									X	X	X
Peripheral blood for chimerism	X ¹³						X									X	X	X
Immune reconstitution panel ¹¹						X										X	X	X
CD34/CD3 cell dose infused			X															
Acute/chronic GVHD assessment				X	X	X	X	X	X	X	X	X	X	X	X	X	X	X
Toxicity assessment			X	X	X	X	X	X	X	X	X	X	X	X	X	X	X	X
Research specimens (voluntary) ¹²	X		X	X		X						X				X	X	X
ANC and platelet recovery ¹⁴																		

Notes

H & PE= history and physical examination

¹Baseline refers to the period prior to conditioning. Assessments should be made within 4 weeks prior to day of conditioning.

²History is only required at baseline.

³Vital signs: blood pressure, pulse rate, respiratory rate and temperature.

⁴Daily during the post-infusion period while hospitalized (recommended) and once weekly after discharge until Day 28.

⁵Serum chemistries panel: electrolytes, BUN, ALT, AST, creatinine, bilirubin, alkaline phosphatase, LDH, albumin. Electrolytes to include sodium, potassium, chloride, carbon dioxide, and calcium.

⁶Infectious disease titers: Cytomegalovirus (CMV) antibody test, hepatitis panel (Hepatitis B including HBsAg, HBcAb; Hepatitis C Ab), HIV including HIV testing, syphilis, Epstein-Barr Virus (EBV) IgG and IgM, herpes simplex virus (HSV) IgG and IgM

⁷To be determined by MUGA or echocardiogram.

⁸Required at baseline. On Days +100, +180 and +365, bone marrow biopsy will be performed if clinically indicated. Other tests and/or imaging studies for response assessment will be performed as clinically indicated.

⁹Females of reproductive potential only.

¹⁰IgG, IgM and IgA.

¹¹Peripheral blood flow cytometry to assess recipient immune reconstitution.

¹²Peripheral blood specimens: draw 15 mL in purple top (EDTA containing) tubes AND 5 mL in blue top (citrate containing) tubes at indicated time points and send to the Biospecimen Processing Core at WVU. At MCW voluntary research specimens will not be collected.

¹³Chimersim testing to be performed prior to study from BOTH donor and recipient at any time point. Chimerism testing should be sorted (lineage specific) to assess myeloid and lymphoid cell chimerism.

¹⁴Record time to neutrophil engraftment defined as first of three consecutive days with ANC $\geq 500 \times 10^9/L$, and platelet engraftment defined as first day of platelet count $\geq 20,000 \times 10^9/L$, without transfusion for 7 consecutive days.

[figure not shown]
¹⁵After day 365, patients will be followed at least yearly for survival, relapse and cause of death for a total of 5 years post transplantation.

8. Drug Formulation and Procurement

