It is the policy of the Mary Babb Randolph Cancer Center to strive for gender and minority patient participation that represents the population of West Virginia in all clinical investigations. Between January 1st 2009 and December 31st 2009, 125 patients were enrolled onto Phase I/II/III trials at the Mary Babb Randolph Cancer Center. Of these patients 73% percent were female (n=92) and 2.4 percent were members of minority ethnic groups. It is anticipated that a similar or greater proportion of patients on this study will be female and/or members of ethnic minorities.

2. Objectives:

2.1. Primary Objectives:

1. Determine the efficacy of an atorvastatin/tacrolimus/methotrexate regimen in preventing grade II-IV acute GVHD in patients undergoing allogeneic hematopoietic stem cell transplantation (HSCT).
2. Assess the safety of an atorvastatin/tacrolimus/methotrexate regimen in patients undergoing allogeneic HSCT.

2.2. Secondary Objectives:

1. To assess rates of chronic GVHD.
2. To assess rates of late onset acute GVHD at days +180 and +365.
3. To assess rates of grade III-IV acute GVHD at days +100, +180 and +365.
4. To assess non-relapse mortality at 100 days post-HSCT.
5. To assess time to successful neutrophil engraftment.
6. To assess time to successful platelet engraftment.
7. To assess incidence of primary and secondary graft failure.
8. To assess incidence of primary and secondary graft rejection.
9. To assess relapse rate of the primary hematological malignancy.
10. To assess lineage specific chimerism kinetics in patients at days +28, +100, +180 and +365.
11. To assess immune reconstitution following transplantation at days +28, +100, +180, and +365.
12. To assess 1 year progression free survival (PFS) and overall survival (OS) following transplantation.
13. To evaluate biologic and genomic markers potentially associated with GVHD and/or atorvastatin.

3. Eligibility Criteria:

3.1. Patient Eligibility Criteria:

1. Patients with a history of a hematological malignancy or bone marrow failure syndrome suitable for allogeneic stem cell transplantation in the opinion of treating transplant physician.
2. Patients aged 18-75 years of age are eligible. Patients with age ≥ 18 and ≤ 50 years will be eligible for myeloablative conditioning (MAC), while patients > 50 years of age, or those with previous history of autologous transplantation, high hematopoietic cell transplant comorbidity index (HCT-CI) score (>2), and baseline diagnosis of hodgkin's

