Joints and Fascia:	 No symptoms	 Mild tightness of arms or legs, normal or mild decreased range of motion (ROM) AND not affecting ADL	 Tightness of arms or legs  Joint contractures, erythema thought due to fascitis, moderate decreased ROM AND mild to moderate limitation of ADL	 Contractures WITH significant decrease of ROM AND significant limitation of ADLs (unable to tie shoes, button shirts, dress self etc.)
Other indicators, clinical manifestations or complications related to Chronic GvHD (check all that apply). Assign a score to it's severity based on functional impact, where applicable (0= none, 1=mild, 2 = moderate, 3= severe)				
 Ascites (serositis) _____  Cardiac conduction defects _____  Cardiomyopathy _____  Coronary artery involvement _____  Other(s): Specify & score _____		 Esophageal stricture or web _____  Eosinophilia > 500 µl _____  Myasthenia Gravis _____	 Nephrotic syndrome _____  Pericardial effusion _____  Peripheral neuropathy _____  Platelets < 100,000/µl _____	 Pleural effusions _____  Polymyositis _____  Progressive onset _____

Based on observations checked in the above table, select the severity of chronic GvHD for this assessment (Check only one)

None

Mild chronic GVHD involves only 1 or 2 organs or sites (except the lung: see below ¶), with no clinically significant functional impairment (maximum of score 1 in all affected organs or sites)

Moderate chronic GVHD involves: (1) at least 1 organ or site with clinically significant but no major disability (maximum score of 2 in any affected organ or site) or (2) 3 or more organs or sites with no clinically significant functional impairment (maximum score of 1 in all affected organs or sites). *¶A lung score of 1 will also be considered moderate chronic GVHD.*

Severe chronic GVHD indicates major disability caused by chronic GVHD (score of 3 in any organ or site). *¶A lung score of 2 or greater will also be considered severe chronic GVHD.*

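### The engraftment thresholds in Section 6.3 and calendar note 14 carry a unit that appears to make both 1000 times too high

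*Combined protocol and SAP*

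**What the plan says.** The protocol defines engraftment in two places, and they agree.

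- **Section 6.3 (Engraftment Assessment).** The neutrophil criterion begins "Neutrophil engraftment will be defined as first of three consecutive days with ANC" and gives the level as "ANC $\geq 500 \times 10^9/L$ post-conditioning regimen induced nadir". The platelet criterion is the first day with "platelet count $\geq 20,000 \times 10^9/L$, without transfusion for 7 consecutive days".
- **Section 7.1, calendar note 14.** Staff are told to record the time to each event. The note gives the same neutrophil threshold, and has "platelet engraftment defined as first day of platelet count" at or above the same 20,000 × 10^9/L.

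These definitions serve secondary objectives 5 and 6 (Schema and Section 2.2). Objective 5 reads "To assess time to successful neutrophil engraftment", and objective 6 is its platelet counterpart. No other section gives a threshold or restates the unit.

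Appendix B, the chronic GVHD scoring form, shows the scale on which the protocol otherwise writes platelet counts. Among its additional indicators or complications it lists "Platelets < 100,000/µl".

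**The concern.** The unit 10^9/L is already a thousand per microlitre. A numeral of 500 or 20,000 in front of it gives a count far above anything the protocol could mean by recovery after a conditioning-induced nadir. A platelet recovery threshold cannot sensibly lie far above a level that the same document flags as low.

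These are the only operative definitions for two time-to-event objectives, and note 14 is the instruction under which the dates are recorded. If a data-entry check or a derivation program followed the text exactly, neither objective would have an event. The trial runs at two institutions, so leaving each site to correct the unit for itself is avoidable.

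**Working it through.** The plan derives no figure here that could be reproduced, so the check is a unit conversion.

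**Inputs**
- ANC threshold: 500 × 10^9/L (Section 6.3 and note 14).
- Platelet threshold: 20,000 × 10^9/L (Section 6.3 and note 14).
- Platelet low-count indicator: 100,000 per microlitre (Appendix B).

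**Formula.** One litre is 10^6 microlitres, so X × 10^9/L = X × 10^9 / 10^6 = X × 1000 per microlitre.

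**Printed thresholds, converted**
- ANC: 500 × 1000 = 500,000 per microlitre.
- Platelets: 20,000 × 1000 = 20,000,000 per microlitre.

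**Comparison with Appendix B**
- 100,000 per microlitre = 100,000 / 1000 = 100 × 10^9/L.
- Printed platelet threshold relative to this: 20,000 / 100 = 200.

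**The same numerals read as per-microlitre counts**
- ANC: 500 / 1000 = 0.5 × 10^9/L.
- Platelets: 20,000 / 1000 = 20 × 10^9/L.
- Printed over re-read value: 500 / 0.5 = 1000 for ANC, and 20,000 / 20 = 1000 for platelets.

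**How far the documents support the re-reading.** For platelets the support is internal. Appendix B writes platelet counts per microlitre, and 20,000 per microlitre lies below its 100,000 indicator, whereas the printed threshold lies 200-fold above it. For neutrophils no section gives a scale for ANC. The inference there rests on the parallel construction: both criteria are defined together in Section 6.3, in the same form and with the same unit, so the same slip is the natural explanation.

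**Where the thresholds are used.** They bear on objectives 5 and 6. Section 9 does not use them in the primary endpoint (grade II-IV acute GVHD by day +100), in either arm's two-stage boundaries, or in the stopping rules on atorvastatin-related grade 3-4 events and relapse. Section 9 also specifies no engraftment analysis.

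**The case against.** The strongest reply is that this is a recognisable slip with little practical reach. Transplant physicians and data managers are very unlikely to wait for 20 million platelets per microlitre. The documents contain no case report form or program, so an actual recording error is only a possibility. Two descriptive objectives out of thirteen are touched, and nothing that decides whether the trial continues or succeeds. This stands, and it is why the severity is low.

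The Appendix B entry is also neither a normal range nor an engraftment criterion. It shows the platelet unit in use and a level treated as low, and it says nothing about neutrophils. That stands too: the intended ANC unit is an inference.

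The exponent might have been misread when the PDF was converted to text. This cannot be fully excluded, since all occurrences passed through the same conversion. But the same exponent appears four times, in two separate places, which makes a misread improbable. The source PDF would settle it.

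Two stronger readings are tempting, and the documents support neither.

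- A reader might infer that the literal text makes primary graft failure 100%. That needs a definition of graft failure as absence of engraftment. Objective 7 names primary and secondary graft failure but no section defines them, so no rate follows.
- A reader might infer that the primary endpoint is compromised, because Section 6.2 words weekly GVHD monitoring as following neutrophil engraftment. The study calendar schedules GVHD assessment from day 7 without reference to engraftment, so assessment does not depend on the threshold being met.

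**Conclusion.** Wrong as written, at low severity. All four printed thresholds (two cell lines, two places) convert to 500,000 neutrophils or 20,000,000 platelets per microlitre. The platelet threshold is 200 times a count that the protocol itself lists as a low-count indicator. If the numerals were meant per microlitre, the error is exactly 1000-fold for both cell lines. That intent is supported by Appendix B for platelets and assumed by analogy for ANC.

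That the printed definitions are unworkable does not depend on the exact factor: counts of this size are not recovery levels that patients would reach. Taken literally, objectives 5 and 6 would have no events. The effect goes no further than that on the documents' own terms.

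**What to change.** In Section 6.3 and in calendar note 14, keep the numerals and correct the unit, so that both places read ANC ≥ 500 per microlitre (0.5 × 10^9/L) and platelets ≥ 20,000 per microlitre (20 × 10^9/L). The sponsor should confirm that this is the intended unit, particularly for ANC, and that data capture and any derivation of engraftment dates at both sites use it.

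The cost is a wording correction in two places and one check of data capture. Sample size, decision boundaries and visit schedule do not change.

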8.1. Atorvastatin (Lipitor® Pfizer)

8.1.1. Drug description

LIPITOR is a synthetic lipid-lowering agent. Atorvastatin is an inhibitor of 3-hydroxy-3-methylglutaryl-coenzyme A (HMG-CoA) reductase. This enzyme catalyzes the conversion of HMG-CoA to mevalonate, an early and rate-limiting step in cholesterol biosynthesis. Atorvastatin calcium is $[R-(R^*, R^*)]-2-(4\text{-fluorophenyl})-\beta, \delta\text{-dihydroxy-5-(1-methylethyl)-3-phenyl-4-[(phenylamino)carbonyl]-1H-pyrrole-1-heptanoic acid}$, calcium salt (2:1) trihydrate. The empirical formula of atorvastatin calcium is $(C_{33}H_{34}FN_2O_5)2Ca \cdot 3H_2O$ and its molecular weight is 1209.42. Its structural formula is: Atorvastatin calcium is a white to off-white crystalline powder that is insoluble in aqueous solutions of pH 4 and below. Atorvastatin calcium is very slightly soluble in distilled water, pH 7.4 phosphate buffer, and acetonitrile; slightly soluble in ethanol; and freely soluble in methanol. LIPITOR Tablets for oral administration contain 10, 20, 40, or 80 mg atorvastatin and the following inactive ingredients: calcium carbonate, USP; candelilla wax, FCC; croscarmellose sodium, NF; hydroxypropyl cellulose, cellulose, NF; Opadry White YS-1-7040 (hypromellose, polyethylene glycol, talc, titanium dioxide); polysorbate 80, NF; simethicone emulsion.

